All data were analyzed using the statistical software package SAS version 15.2 (SAS Institute Inc.). The Kolmogorov-Smirnov test was used to test the normality assumption. The three groups of patients were compared in terms of three outcomes, successful cerclage, good outcomes, and PPROM. For categorical variables, a comparison among the three groups of patients regarding socio-demographics and clinical features was conducted using the Chi-square or Fisher's exact test, as appropriate. For continuous variables, the three groups of patients were compared using the Kruskal-Wallis test or analysis of variance (ANOVA), as appropriate. Within each group, we compared the patients in terms of successful cerclage, good outcomes, and PPROM. A p-value less than 0.05 was considered statistically significant. The predictive power of pre- and post-operation cervix length in identifying successful cerclage was evaluated using receiver operating characteristic (ROC) curves, and the area under the curve (AUC) determined the discriminative ability of the parameters. The optimal cut-off values are derived using Youden's Index.

Results

We included 129 patients with a singleton pregnancies in this study. Three membrane rupture complications occurred during the cervical cerclage procedure (all three cases were in the emergency cerclage group and the pouches were prolapsed). Externally, no uncontrollable bleeding or injury to the bladder and/or rectum occurred during cerclage. The sample size was 129 patients, with 32 in the history-indicated cerclage group (G1), 62 in the ultrasound-indicated cerclage group (G2), and 35 in rescue cerclage group (G3). Only six (4.6%) pregnancies resulted in miscarriage before 20 weeks of gestation. Among these three groups, significant differences were observed in gravidity, parity, history of preterm birth, and history of CI. In group 1, the average gravidity was 4.69 (2.05), whereas in groups 2 and 3, it was much lower at 2.47 (1.83) and 2.23 (3.81), respectively. Similarly, parity was much higher in group 1 than in groups 2 and 3.

We compared the three groups in terms of factors that could affect cervical cerclage success and pregnancy outcomes of cerclage cases. Among these three groups, significant

differences were observed in cerclage week, the time elapsed from cerclage to childbirth, post-operation cervix length, complication rates, successful cerclage and good outcomes (delivery beyond 34 completed weeks).

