The average cerclage week was 14.39 (1.99) in group 1, but the week of cerclage performance was later in groups 2 and 3 (21.47 (2.97) and 20.98 (4.14), respectively).

The average time elapsed from cerclage to childbirth was much longer in group 1, with an average of 143.63 (41.27) days, whereas it was relatively shorter in group 2, with an average of 94.46 (35.16) days. The shortest time elapsed from cerclage to birth was observed in group 3, with an average of 69.82 (49.35) days.

In groups 1 and 2, the percentage of patients with successful cerclage was much higher (90.6% and 88.7%, respectively) than in group 3 (66.7%). Similarly the percentage of patients with good outcomes was much higher for the patients in groups 1 and 2 in comparison with group 3. The earlier cerclage is applied after CI is identified, the longer the time from cerclage to birth.

We also evaluated the effects of preop cervical length, postop cervical length, preop procalcitonin value, preop CRP, cerclage week, and cerclage material on cerclage results for each group separately. Within group 1, we compared the patients who had successful cerclage with the patients who did not in terms of pre-op cx, post-op cx, procalcitonin, CRP, the week of cerclage, and the material of cerclage. We found significant difference in these two groups in terms of the average procalcitonin; however, we only had three patients with unsuccessful cerclage and all three patients had the same procalcitonin values. Therefore, we did not report the p-value for this comparison. Based on this result, although we cannot clearly say that high procalcitonin values reduce cerclage success in the prophylactic cerclage group, the effects of procalcitonin need to be studied on cerclage success in more detail.

In the prophylactic cerclage group, there was also a significant difference between patients with and without PPROM ($p<.0001$). The average post-operation cervix length for patients without PPROM was 34.5 (4.64) mm, whereas the average post-operation cervix length for patients with PPROM was 19.4 (0.85) mm. We concluded that the longer the postoperative cervix length, the lower the probability of PPROM in the prophylactic cerclage group.

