Within group 2, there were significant differences between patients with and without successful cerclage in terms of post-cerclage cervical length and procalcitonin levels. The average post-op cervix length was 26.1 (7.37) mm for the patients with successful cerclage, whereas the average post-op cervix length was 18.0 (9.23) mm for patients without successful cerclage ($p=.015$). The average procalcitonin level was 0.06 (0.03) $\mu\text{g/L}$ for patients without successful cerclage, and was 0.04 (0.02) $\mu\text{g/L}$ for patients with successful cerclage.

In the ultrasound-indicated cerclage group, the mean postoperative cervix length of patients with successful cerclage was longer. In this group, we can say that as the postoperative cervical length increases, the success of the procedure increases.

When we compared the patients with and without PPROM in group 2, we found that there was a significant difference between the groups in terms of post-op cervix length ($p=.010$). Patients with PPROM had a shorter post-op cervix length (18.6 (9.02) mm) than patients without PPROM (26.3 (7.32) mm). We conclude that in the ultrasound-indicated cerclage group, as in the prophylactic cerclage group, the longer the postoperative cervix length, the lower the likelihood of PPROM. In this group, similar to the findings for successful cerclage, there were also significant differences between patients with and without good outcomes in terms of post-op cervix length and procalcitonin levels. The average length of post-op cervix length was 27.4 (6.56) mm for patients with good outcomes, whereas the average post-op cervix length of was 19.6 (8.60) mm for patients poor outcomes ($p<.001$). The average procalcitonin level was 0.05 (0.02) $\mu\text{g/L}$ for patients with poor outcomes, and was 0.04 (0.02) $\mu\text{g/L}$ for patients with good outcomes.

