As a result of our analysis for group 3, we found no significant differences (All p -values $>.05$). Lastly, we used ROC curves to calculate the pre-cerclage and post-cerclage CL cut-off value required to predict if birth could be postponed until after the 28th week of gestation in women with CI. Thus, we extracted significant factors for a successful cervical cerclage for long-term pregnancy sustenance in women with CI. In group 2, we used Youden's Index to determine an optimal cut-off value for the post-operation cervix length and the pre-operation cervix length. For the post-operation cervix length, the optimal cut-off value was determined as 23.87 with sensitivity=0.83, specificity=0.72 (AUC=0.78). The area under curve

(AUC) for the analysis with the pre-operation cervix length was equal to 0.52, meaning that this parameter did not have a predictive power for identifying successful cerclage.

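### The group 2 AUC of 0.52 for pre-operation cervix length rests on at most 7 failures and has no interval, so it cannot show that predictive power is absent

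*Combined protocol and SAP*

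**What the plan says.** The Study Protocol sets as an aim a cut-off for cervical length, both before and after cerclage, to predict birth beyond week 28. The Statistical Analysis Plan says that the "area under the curve (AUC) determined the discriminative ability of the parameters", and that cut-offs come from Youden's Index. It plans no interval or test for the AUC.

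The Results then report, for group 2:

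- Group size: "62 in the ultrasound-indicated cerclage group (G2".
- Success rates in groups 1 and 2: "much higher (90.6% and 88.7%, respectively".
- Post-operation length: "the optimal cut-off value was determined as 23.87 with sensitivity=0.83, specificity=0.72 (AUC=0.78".
- Pre-operation length: the AUC "was equal to 0.52, meaning that this parameter did not have a predictive power for identifying successful cerclage".

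The Results also say that the "effects of preop cervical length, postop cervical length, preop procalcitonin value" and other factors were examined within each group. For group 2 they report "significant differences between patients with and without successful cerclage in terms of post-cerclage cervical length and procalcitonin levels"; pre-operation length is not on that list.

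**The concern.** A point estimate close to 0.5 is read as proof that the measurement carries no information. That reading needs an interval narrow enough to rule out useful discrimination, and with very few failures the interval cannot be narrow. Three readings are possible: no discrimination, weak or moderate discrimination that this sample could not detect, and strong discrimination. A reader given only 0.52 cannot tell which of them the data exclude.

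The sentence matters because it is the only answer the Results give to the pre-cerclage half of a declared aim. The authors are more careful elsewhere: in group 1, with three failures, they withhold a p-value and decline to draw a firm conclusion. The group 2 ROC result carries no such caution.

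**Working it through.** **1. Number of failures.** Inputs from the Results: 62 women, 88.7% successful. 55/62 = 88.71%, which reproduces the reported figure; 54/62 = 87.1% and 56/62 = 90.3% do not. Failures: 62 − 55 = 7. The ROC may use fewer if measurements are missing, so 7 is a maximum.

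**2. Interval for AUC = 0.52.** The AUC cannot be recomputed without patient data, but its precision can be approximated (Hanley-McNeil):

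SE² = [A(1−A) + (n₁−1)(Q₁−A²) + (n₂−1)(Q₂−A²)] / (n₁n₂), with Q₁ = A/(2−A) and Q₂ = 2A²/(1+A).

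A = 0.52 gives A(1−A) = 0.2496, A² = 0.2704, Q₁ = 0.52/1.48 = 0.3514, Q₂ = 0.5408/1.52 = 0.3558.

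- 7 failures, 55 successes: SE² = (0.2496 + 0.4857 + 4.6110)/385 = 0.01389, so SE = 0.118. The 95% CI is 0.52 ± 1.96 × 0.118 = **0.29 to 0.75**. Taking success as the positive class gives SE 0.115 and the same limits to two decimals.
- 6 failures, assuming one failure lacks a measurement, with 54 successes for illustration: SE² = (0.2496 + 0.4048 + 4.5256)/324 = 0.01599, so SE = 0.126 and the 95% CI is **0.27 to 0.77**. With 48 successes the limits are the same to two decimals; the failures drive the width.

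**3. What 0.52 argues against.** Equal-variance binormal simulation, 100,000 samples per setting; power is for a two-sided 5% test of AUC = 0.5.

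| True AUC | Chance of observing ≤ 0.52 (7 vs 55 / 6 vs 54) | Power (7 vs 55 / 6 vs 54) |
|---|---|---|
| 0.60 | 24% / 26% | 14% / 13% |
| 0.65 | 13% / 14% | 26% / 23% |
| 0.70 | 5% / 6% | 42% / 37% |
| 0.75 | 1.6% / 2.2% | 62% / 56% |

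A true AUC of 0.75 or more is hard to reconcile with 0.52. A value of 0.60 or 0.65 is quite compatible, and 0.70 is at the edge.

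**4. Do the post-operation figures fit 7 vs 55?** On an empirical curve, one of sensitivity and specificity must be a multiple of 1/7. The nearest candidates are 5/7 = 0.71 and 6/7 = 0.86, so neither 0.72 nor 0.83 is possible. Multiples of 1/55 also miss: 39/55 = 0.71, 40/55 = 0.73, 45/55 = 0.82, 46/55 = 0.84. The reported pair therefore cannot come from an empirical ROC on exactly 7 and 55.

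**The case against.** **0.52 is close to no discrimination, and the plan named the AUC as its criterion.** Both are true. The sentence is in the past tense and tied to this one analysis, no pre-operation cut-off is built on it, and pre-operation length was not a significant factor in group 2. This supports saying that no evidence was found and that strong discrimination is unlikely. It does not support absence, since the analysis would miss a true AUC of 0.70 more often than not.

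**The AUC sentence does not repeat the words group 2.** The text introduces both cut-offs under group 2, so that is the natural reading. If it covered all groups, there would be about 21 failures (3 + 7 + 11, assuming 22/33 successes in group 3). The interval would be roughly 0.38 to 0.66, which still does not show absence.

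**A reader might infer that the curves used 6 failures and 54 successes.** 5/6 = 0.83 and 39/54 = 0.72 do fit, but 38/53, 36/50, 34/47 and 33/46 also give 0.72, and a smoothed ROC would remove the constraint. The check concerns post-operation length only and says nothing about the pre-operation denominator.

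**A reader might also take the p-value of .015 for post-operation length as confirming 6 failures.** It does not. From the reported means and SDs ("18.0 (9.23) mm for patients without successful cerclage", against 26.1 (7.37) mm in successes), ANOVA gives 0.0099 with 7 vs 55 and 0.0155 with 6 vs 54, favouring 6. The Kruskal-Wallis p-value implied by AUC 0.78 is 0.0165 with 7 vs 55 (0.0147 to 0.0185 over AUC rounding 0.775 to 0.785) and 0.025 with 6 vs 54, favouring 7. The plan allows either test for its three-group comparisons and names none for the within-group ones.

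**Conclusion.** The point holds as a fault of interpretation and reporting. The estimate of 0.52 can stand; the claim of absence cannot. With at most 7 failures the approximate 95% CI is 0.29 to 0.75, or 0.27 to 0.77 with 6. The supported conclusion is that no evidence of predictive power was found, strong discrimination is unlikely, and a true AUC of about 0.60 to 0.70 is not excluded.

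A reader might go further and infer that pre-operation length does predict success, or does so as well as post-operation length. The documents support neither: the interval includes 0.5, and its upper limit with 7 failures lies below the 0.78 reported for post-operation length.

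The denominators of both curves are unstated, and the post-operation one is not an empirical 7 vs 55. The documents do not establish what the counts were.

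Assumptions: the AUC refers to group 2; the interval is a large-sample approximation from summary figures; the tail probabilities and power assume an equal-variance binormal model. Confidence is high on the missing interval and the overstated wording. The change should be made, but no other reported result depends on it.

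**What to change.** 1. State the number of women and of failures behind each ROC curve, which class was taken as positive, and whether the curve was empirical or smoothed. Reconcile the counts with 55/62 and explain any exclusions.
2. Report both AUCs with 95% CIs, by an exact or bootstrap method given the few failures, and add this to the Statistical Analysis Plan's ROC paragraph.
3. Replace the concluding sentence with: *no evidence of predictive power was found for pre-operation cervix length in group 2; with so few failures, weak or moderate discrimination cannot be excluded.*
4. Add a paired comparison of the two AUCs only if the text contrasts the two lengths.

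The cost is two intervals and the denominators from data already held, plus one reworded sentence.
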